7.3 Surgery

The goal of surgical treatment is to resect the tumor with negative margins. All lesions of the trunk and extremities will be treated with conservative resection (minimal wide excision) after pre-operative therapy. Surgical resection should remove as wide a margin of tissue around the tumor as possible without compromising function. If postoperative pathology evaluation reveals positive soft-tissue margins other than bone, nerve, or large blood vessels, this margin should be re-resected if possible. If bone, major blood vessel or nerve is microscopically positive additional radiation should be given as noted in the protocol. Resectability will depend upon the judgment of the operating surgeon. For the extremities, limb salvage procedure is standard of care if achievable. For other anatomic areas, it must be the judgment of the operating surgeon that he/she may reasonably expect to obtain negative margins. Extremity patients who are not resectable without amputation may be amputated, and should complete chemotherapy per protocol.

7.4 Concomitant Medication and Supportive Care Guidelines

7.4.1 Potential Drug Interactions

Pazopanib is primarily metabolized by the human CYP3A4 isoenzyme. Potent CYP3A4 inhibitors and inducers **are prohibited on the trial**.

Medications prohibited during pazopanib therapy that strongly inhibit CYP3A4 include (but are not limited to):

- Antibiotics: clarithromycin, telithromycin, troleandomycin, erythromycin
- HIV: protease inhibitors (ritonavir, indinavir, saquinavir, nelfinavir, amprenavir, lopinavir)
- Antifungals: itraconazole, ketoconazole, voriconazole
- Antidepressants: nefazodone
- Antiarrhythmics: diltiazem, felodipine, nicardipine, quinidine, verapamil

Medications prohibited during pazopanib therapy that strongly induce CYP3A4 include (but are not limited to):

- Glucocorticoids: cortisone (>50 mg), hydrocortisone (>40 mg), prednisone (>10 mg), methylprednisolone (>8 mg), dexamethasone (>1.5 mg)
- Anticonvulsants: phenytoin, carbamezepine, phenobarbital, oxcarbazepine
- HIV antivirals: efavirenz, nevirapine
- Antibiotics: rifampin (rifampicin), rifabutin, rifapentine
- Miscellaneous: St. John's Wort, modafinil, pioglitazone, troglitazone, canertinib, erlotinib, lapatinib

Pazopanib is a weak inhibitor of CYP3A4, CYP2C8, and CYP2D6. Drugs that have narrow therapeutic windows and are substrates for these enzymes **should be administered with**

extreme caution. Because of pazopanib's long half-life, caution should continue to be exercised for at least 14 days after the last dose of pazopanib when administering these medications.

Medications to use with caution that are substrates for these enzymes *and* have narrow therapeutic windows medications include (but are not limited to):

- Ergot derivatives: dihydroergotamine, ergonovine, ergotamine, methylergonovine (potential increased risk for developing ergot toxicity that includes severe vasospasm leading to peripheral as well as cerebral ischemia)
- Neuroleptics: pimozide (potential increased risk for QT interval prolongation, ventricular arrhythmia, and sudden death)
- Antiarrhythmics: bepridil, flecainide, lidocaine, mexiletine, amiodarone, quinidine, propafenone (potential increased risk for QT interval prolongation and Torsade de Pointes)
- Immune modulators: cyclosporine, tacrolimus, sirolimus (potential increased risk for nephrotoxicity and neurotoxicity)
- Miscellaneous: quetiapine, risperidone, clozapine, atomoxetine, simvastatin, bevacizumab, topotecan, short-acting antacids and PPIs.

Pazopanib can prolong the QTc interval. Drugs that are generally accepted to have a risk of causing Torsades de Pointes (see **Appendix E**) should be discontinued or replaced with drugs that do not carry this risk, if at all possible. Subjects who receive potential QTc-prolonging medications (see **Appendix E**) should be monitored closely.

Pazopanib may increase bleeding. Subjects, receiving pazopanib and anticoagulation, should be monitored for bleeding.

Pazopanib may cause decreased glucose. Subjects, receiving pazopanib and hypoglycemia agents, should be monitored for hypoglycemia.

7.4.2 Supportive Care

Anti-Emetics

Routine use of anti-emetics is recommended for subjects due to the highly emetogenic nature of the chemotherapy regimen. Selection of anti-emetics is based on the institution's standard and is at the Investigator's discretion.

Prophylactic Antibiotics

Prophylactic antibiotics for prevention of neutropenic fever may be used at the discretion of the Investigator. Use of prophylactic antibiotics must be recorded in the case report forms.

Growth Factors

Administration of growth factor is required after all chemotherapy cycles:

PEG-filgrastim 6 mg administered as a subcutaneous injection starting 24-48 hours after completion of chemotherapy (may substitute filgrastim 5 mcg/kg/day (rounded to nearest vial

size) administered as a subcutaneous injection starting 24-48 hours after completion of chemotherapy for 10 days, or until white blood count has recovered after nadir (ANC > 10,000)

Transfusion of Blood Products

Depending on the particular setting, red blood cell and platelet transfusions may be appropriate, at the Investigator's discretion and with the subject's consent.

7.5 Duration of Therapy

Treatment should continue until the end of protocol therapy, defined as the completion of all adjuvant treatments following surgical resection of the primary tumor, or until one of the following criteria applies:

- Disease progression,
- Intercurrent illness that prevents further administration of treatment,
- Unacceptable adverse events(s),
- Greater than 3-week delay in therapy due to adverse event
- The subject or legal representative requests to withdraw from the study, or
- Changes in the subject's condition render the subject unacceptable for further treatment in the judgment of the Investigator.

7.6 Duration of Follow-Up

When a subject discontinues the study, a Final Visit will be conducted. All subjects will have one Follow-up Visit approximately 30 days after the Final Visit. This Follow-up Visit does not need to be performed for subjects who have had a Final Visit conducted \geq 30 days after discontinuation of maintenance pazopanib therapy.

Study visits and evaluations will be performed in clinic at Screening and within approximately 72 hours prior to hospital admission for each chemotherapy cycle (neoadjuvant as well as adjuvant). Assessments will include interval history, physical examination, blood counts and chemistries. Radiological assessments including FDG-PET CT, MRI of the primary tumor, and diagnostic CT chest will be performed prior to the 14 day Run-in period of pazopanib versus placebo. After the Run-in period, and prior to commencement of preoperative chemotherapy, subjects will undergo repeat FDG-PET CT and MRI of the primary tumor. After 2 cycles of chemotherapy, FDG-PET CT and MRI of the primary tumor will be repeated. (**Refer to Section 4.3 and Appendix A**). Study procedures may be performed up to approximately 72 hours before or after the scheduled visit date.

Subjects will be evaluated daily during radiation therapy. Following surgery, subjects who remain on pazopanib monotherapy will have study visits and evaluations monthly for the one year duration of therapy, and follow-up visits will be every 3 months for those not on pazopanib. CT of the chest without contrast will be performed every 3 months for the first

year following surgery and MRI (or CT) of the primary site of the tumor will be performed every 6 months.

Following the Final Visit and/or 30-day Follow-up Visit, follow-up will proceed as described in the study calendar (Appendix A) until recurrence or progression. Patients experiencing recurrence or progression will be contacted every 4 months for overall survival, unless the patient has withdrawn consent for the study has ended.

7.7 Dosing Delays/Dose Modifications

Recommendations for pazopanib dose interruptions/modifications in case of specific treatment-emergent AEs are provided in the following sections.

As a general rule, if dose reduction of pazopanib is necessary, the dose should be reduced stepwise by 200 mg at each step, and the subject should be monitored for approximately 10 to 14 days at each dose level. If toxicity does not abate during this monitoring time, the IP may need to be interrupted and/or the dose further decreased with continued monitoring for an additional 10-14 days at each dose level, and so on.

If the toxicity has abated with reduction of the dose and dose re-escalation is considered safe by the Investigator, the pazopanib dose can then be increased step-wise back to the pre-event dose (in 200 mg increments, after monitoring for 10-14 days at each dose level to ensure that toxicity did not recur or worsen).

General: Pazopanib dosing will be modified for adverse events according to the following sections. Reference the following Dose Level table:

Dose Level	Pazopanib
-2*	400 mg daily
-1	600 mg daily
1	800 mg daily

*Patients will be removed from protocol treatment if dose reduction below this level is indicated.

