7.0 TREATMENT PLAN

TREATMENT	PAZOPANIB RUN-IN ^A	CYCLES 1 AND 2 ^B	CYCLES 3 AND 4 ^C	PRE- OP RT ^D	SURGERY ^E	CYCLES 5 AND 6 ^B	POST-OP RT ^F
DOXORUBICIN		75 MG/M2 CIVI OVER 3 DAYS, EACH CYCLE WEEKS 3-8	75 MG/M2 CIVI OVER 3 DAYS, EACH CYCLE WEEKS 9-14	WEEKS 16-21	2-4 WEEKS AFTER COMPLE- TION OF PRE- OPERATIVE THERAPY	75 MG/M2 CIVI OVER 3 DAYS, EACH CYCLE 2-4 WEEKS AFTER SURGERY	2-4 WEEKS AFTER COMPLETION OF CHEMO-THERAPY
IFOSFAMIDE		2 GM/M2 IV, DAYS 1-5, EACH CYCLE WEEKS 3-8 (6-DAY WASHOUT AFTER PAZOPAN -IB	2 GM/M2 IV, DAYS 1-5, EACH CYCLE WEEKS 9-14			2 GM/M2 IV, DAYS 1-5, EACH CYCLE 2-4 WEEKS AFTER SURGERY	

TREATMENT	PAZOPANIB RUN-IN A	CYCLES 1 AND 2B	CYCLES 3 AND 4C	PRE- OP RT D	SURGERY E	CYCLES AND 6B 5	POST-OP RTF
MESNA^I		AFTER EACH DOSE OF IFOS	AFTER EACH DOSE OF IFOS			AFTER EACH DOSE OF IFOS	
PAZOPANIB OR PLACEBO	800 MG PO DAILY, WEEKS 1-2						
PAZOPANIB MAINTEN- ANCE^G							1 WEEK AFTER COMPLETION OF CHEMO/RT (DURATION 52 WEEKS)

A Pazopanib versus placebo run-in 14 days

B Chemotherapy cycles every 21 days. Cycle 1 may not commence until a 6 day washout period of pazopanib has occurred.

C Cycles 3 and 4 will only be given if there is a response to chemotherapy identified on imaging after cycles 1 and 2.

D Pre-operative radiation administration, when given, will consist of external beam 50 Gy in 25 fractions of 2 Gy/fraction over 5 weeks. If the target volume encompasses sensitive structures such as bowel or lung, the dose can be reduced to 45 Gy in 25 fractions of 1.8 Gy without protocol violation.

E Surgery should be planned for 2-4 weeks after completion of pre-operative therapy. Any planned post surgical adjuvant chemotherapy should be initiated only after adequate wound healing has been achieved. Patients who require a delay of greater than 10 weeks from the initial surgery due to inadequate wound healing will be removed from further protocol therapy.

F Post-operative radiation administration, when given, will consist of external beam 50 Gy in 25 fractions of 2 Gy/fraction over 5 weeks, followed by 10 Gy boost (in 5 fractions) to a reduced, or boost, volume. For contaminated or close margins, the boost dose will be 10 - 16 Gy; for microscopically positive margins, 16 - 20 Gy, and for grossly positive margins, 20 – 26 Gy.

For patients who received pre-operative radiation, but have positive surgical margins, 16 – 20 Gy (2Gy x 8 - 10 fractions) will be given by external beam following any planned adjuvant chemotherapy.

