QTc ≥ 500 msec	Discontinue IP and continue follow-up per protocol.
Proteinuria	
UPC <3	Continue pazopanib at the current dose; monitor as clinically indicated
UPC ≥ 3 or 24-h urine protein ≥ 3 g	
Step 1. Interrupt IP.
 
Step 2. Weekly UPC or 24-hr urine protein monitoring until UPC is <3 or 24-hr urine protein is <3 grams. Then restart pazopanib dose-reduced by 200 mg.
 
Step 3. If UPC ≥ 3 or 24-h urine protein ≥ 3g recurs, repeat steps 1 and 2.
 
Step 4. If UPC ≥ 3 or 24-hr urine protein ≥ 3g recurs and the pazopanib dose can no longer be reduced, discontinue pazopanib and continue follow-up per protocol.

Hemorrhage /Bleeding: Investigate and document underlying etiology of the bleeding	
Grade 1	For hemoptysis, interrupt pazopanib and contact the Novartis Study Physician to discuss whether further treatment with pazopanib is appropriate.

	For other Grade I hemorrhage/bleeding events, continue pazopanib at the current dose; monitor as clinically indicated.
Grade 2	Step 1. If pulmonary or GI bleed (other than hemorrhoidal bleeding), discontinue IP and continue follow-up per protocol. Otherwise, interrupt IP until the AE resolved to \leq Grade 1. Step 2. Restart IP; consider reducing dose and monitor as clinically indicated.
Grade 3 or 4, or Recurrent \geq Grade 2 event after dose interruption/reduction.	Discontinue IP and continue with follow-up per protocol.
Venous Thrombosis (DVT, PE)	
Grade 2	Continue IP at the current dose; monitor as clinically indicated
Grade 3	Step 1. Interrupt IP. Step 2. Initiate and monitor anticoagulation as clinically indicated. Step 3. Resume IP at same dose only if all of the following criteria are met: 
 • The subject must have been treated with anticoagulant at the desired level of anticoagulation for at least one week. • No Grade 3 or 4 or clinically significant Grade 2, hemorrhagic events have occurred while on anticoagulation treatment. Subject should be monitored as clinically indicated during anticoagulation treatment and after resuming study treatment. When treating with warfarin, international normalized ratio (INR) should be monitored within three to five days after any change in IP dosing (eg, re-initiating, escalating/de-escalating, or discontinuing IP), and then at least weekly until the INR is stable. The dose of warfarin (or its derivatives) may need to be adjusted to maintain the desired level of anticoagulation

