Grade 4 and/or PE	Discontinue IP and continue follow-up per protocol.
Arterial Thrombosis/Ischemia	
Any Grade	Discontinue IP and continue follow-up per protocol.
Thrombocytopenia: Investigate and document underlying cause	
Grade 1 or 2	Continue IP with current dose; monitor as clinically indicated.
Grade 3 or 4	Step 1. Interrupt IP until toxicity resolves to \leq Grade 2. Step 2. Restart IP dose-reduced by 200 mg and monitor as clinically indicated. If no recovery to \leq Grade 2 or recurrent Grade 3 or 4 thrombocytopenia, discontinue IP and follow-up per protocol.
Anemia: No specific dose reduction rules are indicated for anemia unless due to hemorrhage or bleeding as noted above.	
Palmar-plantar Erythrodysesthesia Syndrome	

Grade 1 Minimal skin changes or dermatitis without pain (erythema, oedema, hyperkeratosis)	1. Continue IP at present dose
Grade 2 Skin changes with pain; limiting instrumental activities of daily living (ADLs) (peeling, blisters, oedema, bleed, hyperkeratosis)	1. Hold IP 2. Treat as clinically appropriate 3. Upon resolution to Level 1 or better restart IP with a dose reduction to 400 mg 4. If recurrent consider a further dose reduction to 200mg or discontinuation
Grade 3 Severe skin changes with pain and limiting self care ADLs	1. Discontinue IP
Other Clinically Significant Adverse Events^b	
Grade 1	Continue IP; monitor as clinically indicated.
Grade 2 or 3, if clinically significant	Step 1. Interrupt IP until toxicity resolves to \leq Grade 1. Step 2. Restart IP dose-reduced by 200 mg and monitor as clinically indicated.
Grade 4	Discontinue IP and continue follow-up per protocol.

a. Well-controlled BP defined as SBP <140 mmHg and mean DBP <90 mmHg.
 b. AEs are graded according to NCI Common Terminology Criteria for Adverse Events v4.0 (NCI CTCAE v4)
 Abbreviations: BP, blood pressure; IP, investigational product.

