7.7.2 Dose Interruptions/Modifications for Hepatotoxicity

AST, ALT and/or Bilirubin	
Isolated AST/ALT elevations between 3X ULN and 8X ULN	Reduce pazopanib dose to 200 mg QD, and monitor weekly until AST/ALT returns to ≤ 2.5 or baseline
AST/ALT >8 X ULN	Hold pazopanib until AST/ALT returns to ≤ 2.5 X ULN or baseline. If the potential benefit of reinitiating pazopanib treatment is considered to outweigh the risk for hepatotoxicity, then consider reintroducing pazopanib at a reduced dose of 400 mg once daily and measure serum liver tests weekly for 8 weeks only after discussion with the PI . If AST/ALT elevations >3 X ULN recur, then pazopanib should be permanently discontinued.
AST/ALT >3 X ULN and concurrent bilirubin elevations >2 X ULN	Permanently discontinue pazopanib.
Mild indirect hyperbilirubinemia, known or suspected Gilbert's syndrome, and elevation in AST/ALT >3 X ULN	Continue pazopanib, but monitor weekly until AST/ALT returns from >3 X ULN to grade 1 (NCI CTCAE) or baseline.

Severe hepatic impairment, defined as bilirubin >3 X ULN, regardless of any level ALT	Permanently discontinue pazopanib.
---	------------------------------------

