7.8 Criteria for Evaluability and Removal/Withdrawal from Treatment

Criteria for evaluability of the Trial

- Patients must have received a total of at least 80% of the intended dose of doxorubicin, ifosfamide, and pazopanib to be evaluable for the trial. If less than this amount is received, the patient may remain on the study, but will not be evaluated for primary endpoints.

Criteria for stopping therapy:

- Substantial non-compliance with the requirements of the study.
- Any adverse event which, in the Investigator's opinion, requires termination of the study medication.
- Disease progression, unless at the discretion of the Investigator (in collaboration with Novartis) continued treatment with study drug is appropriate.
- The patient would benefit from additional radiation therapy beyond that specified in the protocol.
- Request by the patient or a legal representative/relative to stop the treatment.
- The patient presents with a beta-HCG test consistent with pregnancy. Pregnancy will be reported along the same timelines as a serious adverse event.
- The patient uses illicit drugs or other substances that may, in the opinion of the Investigator, have a reasonable chance of contributing to toxicity or otherwise interfering with results.
- The development of a second malignancy that requires treatment, which would interfere with this study.
- The patient is lost to follow-up.
- Interruption in administration of pazopanib or chemotherapy for greater than 3-week delay.
- Development of an intercurrent illness or situation which would, in the judgment of the Investigator, affect assessments of clinical status and study endpoints to a significant degree.

Criteria for study withdrawal:

- Study closure.
- Patient decision to withdraw from both study therapy and follow-up.

The Investigator will make every reasonable effort to keep each patient in the study unless it is in the patient's best interest to discontinue participation. If a patient is removed from the study or declines further participation, all End of Treatment evaluations should be performed if the patient is willing and able to be assessed. A description of the reason(s) for withdrawal from the study will be recorded on the case report form (CRF). The Investigator should also ensure that all patients are followed up for survival and recurrence after the Final Visit.

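### Section 7.7 takes patients off protocol treatment if pazopanib must go below 400 mg, but Section 7.7.2 orders dosing at 200 mg for isolated AST/ALT of 3-8x ULN

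*Combined protocol and SAP*

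**What the plan says.** Section 7.7 lists three pazopanib levels: 800, 600 and 400 mg daily. The footnote to the lowest reads: "Patients will be removed from protocol treatment if dose reduction below this level is indicated". The text above the table links it to the toxicity sections that follow: "Pazopanib dosing will be modified for adverse events according to the following sections. Reference the following Dose Level table".

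Three later rules bear on that floor:

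- **Section 7.7.2, isolated AST/ALT 3-8x ULN:** "Reduce pazopanib dose to 200 mg QD, and monitor weekly until AST/ALT returns to" 2.5 or baseline.
- **Section 7.7.1, Table 1, Grade 2 palmar-plantar erythrodysesthesia:** after a hold and a restart at 400 mg, "If recurrent consider a further dose reduction to 200mg or discontinuation".
- **Section 7.7.1, Table 1, proteinuria:** if the finding "recurs and the pazopanib dose can no longer be reduced, discontinue pazopanib and continue follow-up per protocol". No lowest dose is given in that row.

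The footnote's term, protocol treatment, is not defined. Section 7.5 uses a near-identical term for the whole course: "the end of protocol therapy, defined as the completion of all adjuvant treatments following surgical resection of the primary tumor". Note E to the Section 7.0 treatment table says that patients whose wound healing delays adjuvant chemotherapy too long "will be removed from further protocol therapy".

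Section 7.8 requires "at least 80% of the intended dose of doxorubicin, ifosfamide, and pazopanib to be evaluable for the trial". Section 11.0 repeats the 80% limit for all three drugs.

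**The concern.** A patient on pazopanib with isolated AST/ALT of, say, 5x ULN meets the trigger in Section 7.7.2 and is to continue at 200 mg. That dose is below level -2, so the Section 7.7 footnote also applies and the patient is to come off protocol treatment. Two sites that both follow the protocol could handle the same laboratory result differently, in a safety instruction of a multi-center trial.

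The event is not remote. Section 2.4 lists ALT and AST increases among the most frequent grade 3 events on pazopanib in the soft tissue sarcoma phase III study, and among the commonest adverse events leading to permanent discontinuation. Most exposure to the conflict comes in maintenance, which lasts a year with regular hepatic panels. In the run-in the conflict can also decide whether a patient counts for the primary endpoints, and how often depends on what protocol treatment covers.

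**Working it through.** **1. The rules side by side**

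| Place | Trigger | Action | Against the 400 mg floor |
|---|---|---|---|
| 7.7 footnote | Dose below 400 mg indicated | Removal from protocol treatment | Sets the floor |
| 7.7.2 | Isolated AST/ALT 3-8x ULN | 200 mg daily, weekly monitoring | Below it, mandatory |
| 7.7.2 | AST/ALT >8x ULN, after a hold | Possible restart at 400 mg | At it |
| Table 1 | Recurrent Grade 2 palmar-plantar erythrodysesthesia | Consider 200 mg or stop | Below it, optional |

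Going from 800 to 200 mg is (800 - 200)/200 = 3 steps of 200 mg. The table holds only two reductions. Section 7.7.2 also gives a lower dose for 3-8x ULN than the possible restart dose after >8x ULN, so a site cannot infer the intended floor from the surrounding rows.

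**2. Proteinuria, as a consequence**

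Reductions available from 800 mg: (800 - 400)/200 = 2 with a 400 mg floor, and (800 - 200)/200 = 3 with a 200 mg floor. The row is not wrong in itself, but its stopping point depends on the same answer.

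**3. Run-in evaluability**

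Inputs: 800 mg daily for 14 days (Section 7.1.1) and the 80% limit (Sections 7.8 and 11.0). Assumption: the intended pazopanib dose for this limit is the run-in total, 14 x 800 = 11,200 mg. For a change starting on day d:

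- 200 mg branch: [800(d - 1) + 200(15 - d)] / 11,200
- removal branch: 800(d - 1) / 11,200

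| Day d | 200 mg branch | Removal branch |
|---|---|---|
| 11 | 8,800 mg, 78.6% | 8,000 mg, 71.4% |
| 12 | 9,400 mg, 83.9% | 8,800 mg, 78.6% |
| 13 | 10,000 mg, 89.3% | 9,600 mg, 85.7% |
| 14 | 10,600 mg, 94.6% | 10,400 mg, 92.9% |

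*If removal stops pazopanib only:* both branches fail through day 11 and both pass on days 13 and 14. They split on day 12 alone.

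*If removal also stops the chemotherapy:* the removal branch has no on-protocol doxorubicin or ifosfamide and fails on every day. The 200 mg branch passes on days 12, 13 and 14, assuming chemotherapy is then given in full. The split is on 3 days.

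The one scheduled on-drug liver test in the run-in is at the end of week 2. With the 72-hour window in Section 7.6 it can fall as early as 14 - 3 = day 11, so these days can be reached.

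**4. Maintenance exposure**

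Hepatic panels in one year: 52/4 = 13 on the four-weekly schedule in Appendix A, or 12 if monthly (Sections 7.1.1 and 7.6). Patients randomized to pazopanib: 21 x 2/3 = 14. Only those with a partial response may opt for maintenance (Section 11.4).

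**The case against.** The strongest reply is that the specific rule governs. Section 7.7 calls its contents recommendations and its stepwise reduction a general rule, then defers to the sections that follow. Section 7.7.2 is the dedicated liver section. A site could reasonably follow it and treat the footnote as lacking a cross-reference. That reading is possible, but the text does not establish it: the next sentence sends the reader back to the dose level table, and neither section exempts liver events.

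Other points have some force:

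- Both branches cut exposure. One stops the drug and the other gives a quarter of the starting dose with weekly monitoring, so neither leaves the patient on full dose. The instructions are still incompatible.
- The 200 mg entry in Table 1 is only an option. A site that stops pazopanib there satisfies both rules, so this is a weaker conflict than the liver row.
- The run-in split is an edge case. The end-of-week-2 panel may be drawn at or after the last dose, and the wider reading of protocol treatment is strained for a footnote under a table that lists only pazopanib. The day counts rest on stated assumptions and do not carry the conclusion.
- Dose modifications are reviewed at bi-monthly meetings (Section 9.2), so divergent handling should surface, though only after the event.

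**Conclusion.** The concern holds. Section 7.7 and Section 7.7.2 give incompatible actions for the same isolated AST/ALT of 3-8x ULN, and nothing in the documents resolves them. This is an error in a safety instruction as written, and it must be corrected. The Table 1 option is related and weaker, and the proteinuria row is a consequence.

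In the run-in, the effect on evaluability is confined to one start day (day 12) if removal stops pazopanib only, and to three (days 12 to 14) if it also stops chemotherapy. Both counts assume an intended run-in dose of 11,200 mg. In maintenance there are 12 to 13 scheduled panels per patient-year at which the conflict could arise. At most about 14 patients are randomized to pazopanib and fewer will enter maintenance. With no stated rate of AST/ALT 3-8x ULN, the number affected cannot be computed.

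**What to change.** Amend Section 7.7 so that the dose level table and its footnote agree with the 200 mg liver order in Section 7.7.2 and the 200 mg option in Table 1, and state which prevails. Say in the footnote whether protocol treatment means pazopanib only or also the chemotherapy. Carry the resulting floor into the proteinuria row. Which rule is right is for the investigator and the drug supplier to decide. The cost is amendment wording, with no added patients or staff.

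A separate, minor item can go in the same amendment. For QTc of 500 msec or more, Table 1 stops the drug and continues follow-up, while Section 7.1.1 removes the subject from the study when the repeat ECG confirms it. The maintenance ECG times also differ between Section 4.3, Section 7.1.1 and Appendix A, and the maintenance cycle length that Section 4.3 relies on is not defined, although visits are set at every 4 weeks or monthly. Aligning the times may add or remove an ECG per maintenance patient, depending on those chosen.
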